### 7.7.3 ECG Evaluations

Descriptive statistics for each parameter and change from baseline (from protocol 093-045 or 093-046) values will be displayed at each scheduled visit (i.e. Visit 3-Visit 7) for each ECG parameter.

The number and percentage of subjects with QTc-F values in the categories as defined in Section 5.3.2 will be summarized.

- QTc-F >500 ms at any post-baseline time point not present at baseline
- QTcF >480 ms at any post-baseline timepoint not present at baseline
- QTc-F >450 ms at any post-baseline time point not present at baseline
- Change from baseline in QTc-F  $\geq$ 60 ms for at least 1 post-baseline measurement
- Change from baseline in QTc-F  $\geq$ 30 ms for at least 1 post-baseline measurement, but <60 ms for all post-baseline measurements

This categorical analysis will be also performed for QTc-B.

The number and percentage of subjects with ECG abnormalities will be presented in the categories of overall, rhythm, conduction, morphology, myocardial infarction and the presence of ST, T, and U wave abnormalities.

Listing of 12-Lead ECG Measurements, Abnormality Findings and Overall Interpretation, and 12-Lead ECG collections will be provided.

#### **7.7.4 Vital Signs**

Observed values and change from baseline period (Visit 1-2 in 093-045 or 093-046) in each vital sign parameter will be summarized at baseline and by visit. A listing of vital signs will be provided. Height will only be summarized at baseline and end of study.

In addition, the number and percentage of subjects meeting sponsor defined PCS vital sign values (outlined in Table 3) will be summarized for 1-Year Open-Label Period and Post-1-Year Open-Label Period.

In addition a listing of subjects meeting any of the PCS vital signs criteria defined by the sponsor will be provided.

#### **7.7.5 Orthostatic Effects**

The number and percentage of subjects who had orthostatic effects (hypertension and tachycardia in Section 5.3.2) will be summarized from Visit 1 (Day 0) until the End of Study or Early Termination Visit for the ITT population.

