Abbreviations: A=Electronic Data Capture (Inform); B=Laboratory Information Management System (LIMS); C=Core Lab Over-Read; C-SSRS=Columbia Suicidality Severity Rating Scale; EOS=End of Study; ET=Early Termination; MADRS=Montgomery-Asberg Depression Rating Scale; NTx=N-telopeptides of type I collagen cross-links; SCN=Screening; 25-OHD=25-hydroxyvitamin D; TSH=thyroid stimulating hormone; PGI=Patient Global Impression; PTH=parathyroid hormone; QOLIE-31=31-Item Quality of Life in Epilepsy.

- a. Demographic information, medical history, psychiatric history, medication history, magnetic resonance imaging/computerized tomography scans, electroencephalogram data, HLA-B\*1502 genotyping, and Hepatitis B/C screen results collected during the screening visit of Protocols 093-045 or 093-046 will apply for this study as well.
- b. Clinic visits to occur at intervals of 3 months during the post-1-year part.
- c. Letters in this column identify the computerized systems that will be used in this protocol (Appendix IX in protocol).
- d. The symbol “•” represents procedures performed at Visit 9 of Protocols 093-045 or 093-046, the results of which will apply to Visit 1 of the present study as well. These procedures do not have to be repeated.
- e. In street clothes without shoes and jacket/coat.
- f. Fasting labs.
- g. These assessments are not required to be performed if this visit falls in the post-1-year part of the study.
- h. If this visit falls in the post-1-year part of the study, this assessment may be performed only if clinically indicated (per Investigator judgement on a previously noted abnormality).
- i. Includes serum 25-OHD, PTH, osteocalcin, bone-specific alkaline phosphatase, and urinary NTx.
- j. At Visit 5 only.
- k. Every 6 months (i.e. Visits 7, 9, 11, 13, etc.).
- l. Only in subjects ≥18 years at time of signing informed consent in Protocols 093-045 or 093-046.
- m. Only for subjects who discontinue study during the post-1-year part of study.
- n. Fill out “since last visit” scale (Appendix VII in protocol).
- o. Only for subjects who discontinue study during the 1-year part of study.
- p. Only for subjects who continue into the post-1-year part of the study.

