### 5.3.2. Safety Endpoints

#### Adverse Events

All AEs will be coded using Medical Dictionary for Regulatory Activities (MedDRA), Version 13.1.

Treatment-emergent adverse events (TEAEs) will be defined as:

- AEs that occurred on or after the first dose of study drug during this protocol,
- AEs with a missing start date and a stop date on or after the first dose of study drug during this protocol, or
- AEs with both a missing start and stop date.

Adverse events whose relationship is assessed as “not related” will be grouped as “unrelated.” Otherwise, adverse events assessed as “unlikely,” “possible,” “probable,” or “definite,” unknown or missing will be grouped as “potentially related.” Further, if a subject reports more than one AE within the same treatment regimen, system organ class (SOC) and preferred term (PT), and any are related, it will be summarized as related.

If a subject has more than one occurrence of an event within a SOC and/or PT, the subject incidence summaries will count each subject only once within that SOC and/or PT. In the case of more than one event within a SOC and/or PT, the event with the highest severity will be summarized in the by-severity summaries and the one with the strongest relationship will be summarized in the by-relationship summaries.

TEAEs will be sorted by SOC in alphabetical order and then by PT sorted by decreasing frequency, with preferred terms with the same frequency sorted in alphabetical order.

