### 12-Lead ECG

Observed values and change from baseline will be summarized for each visit, where change from baseline is the result of interest minus the baseline result (Visit 2 from protocol 093-045 or 093-046).

The number and percentage of subjects with QTc-F values in the following categories will be identified:

- QTc-F >500 ms at any postdose time point not present at baseline
- QTc-F >480 ms at any postdose time point not present at baseline
- QTc-F >450 ms at any postdose time point not present at baseline
- Change from baseline in QTc-F  $\geq$ 60 ms for at least 1 postdose measurement
- Change from baseline in QTc-F  $\geq$ 30 ms for at least 1 postdose measurement, but <60 ms for all postdose measurements.

This categorical analysis will be also performed for QTc-B.

The incidence of specific ECG abnormalities will also be identified for the following categories:

- Overall abnormalities
- Rhythm abnormalities
- Conduction abnormalities
- Morphology abnormalities
- Myocardial infarction
- Presence of ST Segment abnormalities
- Presence of T wave abnormalities
- Presence of U wave abnormalities

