### Orthostatic Effects

The number and percentage of subjects who experienced orthostatic hypotension and orthostatic tachycardia will be summarized. Orthostatic effects can be determined for a vital sign, by examining the difference between positions.

(Standing result during the interval of interest)- (Supine result during the interval of interest)

Orthostatic hypotension is having a difference of ≤ -20 mmHg in systolic or ≤ -10 mmHg in diastolic blood pressure. Orthostatic tachycardia will be defined as a difference in heart rate ≥ 20 beats per minute and the standing heart rate >100 beats per minute after the subject was standing for at least 2-4 minutes.

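### The orthostatic summary starts at Visit 1, a parent-study reading taken before the first open-label dose, and the QTc rules do not clearly exclude the matching ECG

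*SAP*

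**What the plan says.** **Orthostatic effects.** SAP 5.3.2 (Orthostatic Effects) sets the endpoint: "The number and percentage of subjects who experienced orthostatic hypotension and orthostatic tachycardia will be summarized". The blood-pressure criterion is a standing-minus-supine difference: "Orthostatic hypotension is having a difference of ≤ -20 mmHg in systolic or ≤ -10 mmHg in diastolic blood pressure". Neither sentence refers to a baseline value or to the first dose. SAP 7.7.5 gives the analysis window: "hypertension and tachycardia in Section 5.3.2) will be summarized from Visit 1 (Day 0", and the window closes at the end-of-study or early termination visit.

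**Source of the Visit 1 values.** In the SAP 5.1 schedule, vital signs and the 12-lead ECG carry a bullet at Visit 1, not an X. Footnote d explains that the bullet "represents procedures performed at Visit 9 of Protocols 093-045 or 093-046, the results of which will apply to Visit 1 of the present study", and that these procedures need not be repeated. Study drug is first dispensed at Visit 1, and SAP 3.1 places the starting dose at the beginning of the 1-Year Open-Label Period.

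**QTc categories.** SAP 5.3.2 (12-Lead ECG) has "QTc-F >500 ms at any postdose time point not present at baseline". SAP 7.7.3 has "QTc-F >500 ms at any post-baseline time point not present at baseline", and says that its categories are those of 5.3.2. Under SAP 5.3.2 and 6.1 the safety baseline is parent Visit 2 (Day 0).

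**Adverse events, for comparison.** The main treatment-emergent criterion in SAP 5.3.2 is "AEs that occurred on or after the first dose of study drug during this protocol".

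**The concern.** The primary objective (SAP 2.1) is safety and tolerability in the two open-label periods. An incidence table for that objective should count findings that arise after open-label dosing begins. The adverse event rule does this explicitly. The orthostatic window starts one assessment too early, and that assessment belongs to the parent study.

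The Visit 1 reading is not drug-free, since the parent studies also gave eslicarbazepine acetate. The problem is attribution: a finding from the end of double-blind treatment could appear as an open-label finding. The orthostatic count would then cover a different window from the adverse event tables in the same report.

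**Working it through.** The SAP states no orthostatic or QTc rate, so there is no figure to reproduce. The check has three parts.

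**1. Is a Visit 1 reading inside the orthostatic window and before dosing?**
- Inside the window: 7.7.5 begins at Visit 1 (Day 0).
- Before dosing: the reading is from parent Visit 9 (5.1, footnote d), and open-label drug is first dispensed at Visit 1.
- Not excluded: the 5.3.2 definition looks only at the difference between positions at one assessment.

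So an any-time count includes it.

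**2. Is the Visit 1 ECG excluded from the QTc categories?**
- 7.7.3 counts post-baseline values. With baseline at parent Visit 2, the Visit 9 ECG carried to Visit 1 is literally post-baseline.
- 5.3.2 counts postdose values but does not say which dose. The Visit 9 ECG follows parent-study dosing, so this word does not clearly exclude it either.
- The condition that a value must not be present at baseline removes only findings already there at parent Visit 2. It does not remove those that first appeared during double-blind treatment.

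**3. How large could the orthostatic effect be?** Assumptions: a constant per-visit probability q, independent between visits, and all scheduled visits attended. For k open-label assessments:
- proportion ever affected without Visit 1: 1 − (1 − q)^k
- with Visit 1: 1 − (1 − q)^(k+1)

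From the schedule, k = 6 for Visits 2 to 7. Visits are three-monthly after Month 12, so Month 36 is Visit 15 and Visits 2 to 15 give k = 14. Month 36 is an assumed follow-up, because the post-1-year period has no fixed end.

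| q (assumed) | k = 6: without → with Visit 1 | Relative rise | k = 14: without → with Visit 1 | Relative rise |
|---|---|---|---|---|
| 2% | 11.4% → 13.2% | 15.5% | 24.6% → 26.1% | 6.1% |
| 3% | 16.7% → 19.2% | 15.0% | 34.7% → 36.7% | 5.6% |
| 5% | 26.5% → 30.2% | 13.9% | 51.2% → 53.7% | 4.8% |

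For example, at q = 2% and k = 6: 1 − 0.98^6 = 0.114 and 1 − 0.98^7 = 0.132.

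The relative effect is larger for early dropouts. A subject who leaves after Visit 2, ignoring any early termination visit, has two assessments in the window where only one follows dosing. If findings recur in the same subjects, Visit 1 adds fewer new cases than the table shows.

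For ECG, Visits 3 to 7 give 5 assessments, or 6 with Visit 1. If the Visit 1 ECG were counted, the same formula gives 9.6% → 11.4% at q = 2% and 22.6% → 26.5% at q = 5% for a category that needs one qualifying value.

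**Direction.** Dropping Visit 1 can only lower orthostatic incidence or leave it unchanged. QTc counts can move either way. Take a subject with a change of at least 60 ms at parent Visit 9 and changes of 30 to 59 ms on open-label drug. With Visit 1 counted, the subject falls in the higher change category. Without it, the subject moves into the category that requires at least 30 ms once and below 60 ms throughout.

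**The case against.** **The orthostatic table may be by visit.** SAP 7.7.5 does not say that it is a single any-time count. The 5.3.2 definition speaks of an interval of interest, vital signs are summarized by visit in 7.7.4, and 7.6 uses a similar from-visit-to-end-of-study phrase for the Patient Global Impression, where a by-visit summary is meant. In a by-visit table Visit 1 has its own row and nothing is miscounted. This stands as a possible reading, so a reader who infers that the miscount is certain goes further than the text. It does not settle the matter: 7.7.5 counts subjects who had an effect across a stated span, and 7.7.8 uses the same form of window for the suicidality scale without saying by visit.

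**Hypertension is a slip.** This stands. A reader might infer a second, undefined endpoint, but 7.7.5 points to 5.3.2, which defines only orthostatic hypotension and tachycardia. The word needs correcting and has no further consequence.

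**The QTc wording may not describe two windows.** A reader might infer that 5.3.2 uses an open-label window and that 7.7.3 widens it to take in double-blind ECGs. The documents do not support this. 7.7.3 defers to 5.3.2, and 5.3.2 does not tie its wording to the first 093-050 dose, so the two terms could cover the same values. The by-visit ECG display is limited to Visits 3 to 7, and SAP section 1 confines the plan to 093-050 data, both of which count against pooling in parent ECGs. However, the visit limit is stated for the descriptive statistics and not for the categories, and footnote d makes the Visit 9 result a Visit 1 result of this study. What remains is an ambiguity in both sections.

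**The outputs are descriptive.** No test or decision rule depends on these counts, and listings of vital signs and ECGs are planned. That limits the consequence but does not remove the attribution problem in tables that serve the primary objective.

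**Conclusion.** The point holds as a window that needs defining. For orthostatic effects, the text admits a reading taken before open-label dosing, and on the natural any-time reading it would be reported as an open-label finding. For QTc, neither section clearly excludes the carried-over ECG, and the documents do not show that it will be counted.

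The true size cannot be derived from the documents. At assumed independent per-visit rates of 2% to 5%, the relative rise in orthostatic incidence is about 14% to 16% over the first year (1.8 to 3.7 percentage points) and about 5% to 6% with follow-up to Month 36 (1.5 to 2.4 points). Within-subject recurrence would make it smaller, and early dropout larger. No inferential result is affected. The change is worth making because the tables serve the primary objective and the correction costs very little.

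**What to change.** - **One window for incidence counts.** In the Orthostatic Effects and 12-Lead ECG parts of SAP 5.3.2, and in 7.7.3 and 7.7.5, state that counts use assessments after the first 093-050 dose through end of study or early termination. Editing 7.7.3 alone would not be enough, because 5.3.2 does not name the dose either.
- **Visit 1.** Show it only as a separate pre-dose reference row. Exclude it from the counts by visit label as well as by date, because drug is dispensed at Visit 1 and the dates may coincide.
- **Reference for change.** Keep parent Visit 2.
- **Wording.** In 7.7.5, replace hypertension with hypotension, and say whether the table is by visit, any-time, or both.

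The cost is a few words in four places and one condition in the programs. No new data are needed. Orthostatic incidence would stay the same or fall, and QTc category counts could shift in either direction.

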#### **7.7.6 Physical and Neurological Examinations**

The physical and neurological examinations of subjects at beginning of the study and end of study will be summarized by presenting the number and percentage of subjects with normal and abnormal findings in each body area (skin/extremities, EENT, head/neck, etc.) for the ITT population.

Listing of physical examination findings and neurological examination findings will be provided.

#### **7.7.7 Concomitant Medication**

Other than the study drug, any medication taken by subjects during the course of the study will be considered concomitant. The number and percentage of subjects using each concomitant medication will be summarized according to the WHO Drug Class and preferred term for concomitant AED and non-AED medication separately. Subjects with multiple uses of a concomitant medication will be counted once for a given WHO Drug Class and Preferred term.

Listing of concomitant AED, non-AED medications, prior medication, and rescue and emergency medication will also be presented.

#### **7.7.8 Columbia-Suicide Severity Rating Scale (C-SSRS)**

Results from the C-SSRS assessments will be summarized by presenting the number and percentage of subjects with any suicidality, suicidal behavior and type of behavior, and any suicidal ideation and type of ideation.

Shifts in suicidal ideation from baseline to worst post-baseline result will be presented. Worsening ideation is reflected in shifts from lower to higher values.

C-SSRS will be summarized from Visit 1 until the End of Study or Early Termination Visit for the ITT population.

Listing of the C-SSRS assessments will also be presented.

